3.2 Secondary Objectives

- Monitor changes in vital signs and arterial blood gas (ABG) parameters at baseline, 2, 6, 12, and 24 hours.

- Assess sedation depth using the Richmond Agitation-Sedation Scale (RASS) at the same time points.
- Measure patient comfort during NIV via Visual Analogue Scale (VAS, 0–10).

4. Study Design

This single-center, prospective interventional pilot study will enroll consecutive AE-COPD patients requiring NIV. After informed consent, eligible patients receive isoflurane sedation via AnaConDa® integrated into a dual-limb NIV circuit. Continuous safety monitoring will guide dose titration. An interim analysis after 10 patients will inform potential early termination for futility or safety concerns.

5. Study Population

5.1 Inclusion Criteria

- Age \geq 18 years
- Confirmed COPD exacerbation with hypercapnic respiratory failure
- Indication for NIV (BiPAP mode)

5.2 Exclusion Criteria

- Hypersensitivity to isoflurane or volatile anesthetics
- History of malignant hyperthermia
- Severe hepatic dysfunction
- Contraindications to NIV (e.g., facial trauma, uncontrolled secretions)
- GCS $<$ 12 or inability to protect airway
- Hemodynamic instability unresponsive to fluids
- Pregnancy or recent upper airway surgery/tracheostomy

6. Intervention

Isoflurane infusion will be initiated at 1.5 mL/h via syringe pump (Infusia SP7s®, Fresenius Kabi). The AnaConDa® device is placed between mask and ventilator Y-piece, with scavenging on expiratory limb. Fresh gas flow (FGF) is set at patient minute ventilation plus 0.5 L/min. Target $F_{et}\%$ (end-tidal concentration) is 0.3–0.5 vol% for light sedation. NIV settings:

- Pressure support: 8–20 cm H₂O (titrated to 10 mL/kg IBW)
- PEEP: 4–6 cm H₂O
- RR: 12–16 breaths/min (I:E 1:3–1:4)
- FiO_2 : 30–40% (titrate to SpO_2 88–94%)

Sedation depth will be adjusted based on RASS, targeting -1 to -2 . Excessive sedation ($\text{RASS} \leq -3$) prompts immediate cessation (failure event).

7. Study Assessments

Assessment	Baseline	2 h	6 h	12 h	24 h
Vital signs (HR, BP, RR)	✓	✓	✓	✓	✓
ABG parameters	✓	✓	✓	✓	✓
RASS	✓	✓	✓	✓	✓
VAS comfort score	✓	✓	✓	✓	✓
Intervention failure	—	✓	✓	✓	✓

8. Safety Monitoring

- Continuous pulse oximetry, ECG, non-invasive BP every 15 minutes for first hour, hourly thereafter.
- Monitor for hypotension ($\text{SBP} < 90 \text{ mmHg}$), bradycardia ($\text{HR} < 50 \text{ bpm}$), respiratory depression ($\text{RR} < 10 \text{ breaths/min}$).
- ABG review for hypercapnia or hypoxemia.
- Report serious adverse events (SAEs) within 24 hours to DSMC.

9. Statistical Analysis Plan

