9.4 Secondary Outcomes

- Continuous variables (vitals, ABG, RASS, VAS):
Summarize as mean \pm SD or median (IQR) as appropriate.
Paired t-test (or Wilcoxon signed-rank) comparing baseline vs. each time point.
- Categorical variables (intubation, excessive sedation):
Chi-square or Fisher's exact test.
- Time-to-intubation: Kaplan–Meier curve with log-rank test.

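### If the 12–16/min NIV rate is machine-delivered, the RR < 10 limit cannot register respiratory depression on NIV, and the hypercapnia check has no reference to baseline

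*Combined protocol and SAP*

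**What the plan says.** Section 6 (Intervention) gives the NIV settings as a list. One line reads "RR: 12–16 breaths/min (I:E 1:3–1:4" and stands with PEEP and FiO2. Another reads "Pressure support: 8–20 cm H₂O (titrated to 10 mL/kg IBW". On mode, Section 5.1 says only "Indication for NIV (BiPAP mode"; it does not say whether breaths are spontaneous, timed or both.

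Section 8 (Safety Monitoring) sets the rate limit: "respiratory depression ($\text{RR} < 10 \text{ breaths/min". It does not say which breaths are counted. For blood gases it asks for "ABG review for hypercapnia or hypoxemia", with no level and no comparison with baseline. Section 5.1 requires "Confirmed COPD exacerbation with hypercapnic respiratory failure" in every patient.

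Two other provisions bear on the point. Section 3.2 makes serial change an objective: "Monitor changes in vital signs and arterial blood gas (ABG) parameters at baseline, 2, 6, 12, and 24 hours". Section 9.4 analyses it by "Paired t-test (or Wilcoxon signed-rank) comparing baseline vs. each time point".

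**The concern.** Loss of respiratory drive is a central risk when hypercapnic patients with an unprotected airway are sedated, and the synopsis names safety, including vital signs and ABG changes, as a secondary objective. Section 8 offers two respiratory checks beyond oximetry. On the natural reading of Section 6, the first cannot be triggered while the machine is delivering breaths. The second names a state that patients are already in before isoflurane starts.

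A site that followed the plan faithfully could therefore report no respiratory depression in a patient whose own breathing effort had largely stopped. That zero could be taken as evidence of safety at the 10-patient DSMC review and in the final report. The RR means compared with baseline in Section 9.4 would have the same floor of 12/min. The plan gives no baseline RR, so the effect of that floor on the means cannot be sized.

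**Working it through.** The plan gives no figure of its own on this point to reproduce. The check sets its settings beside its limits.

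**Inputs.** Set rate 12–16/min with I:E 1:3–1:4 (Section 6); tidal volume target 10 mL/kg IBW (Section 6); limit RR < 10/min (Section 8); hypercapnic failure at entry (Section 5.1); 20 patients, with a review at 10 (Sections 9.1 and 9.6); ABG at baseline, 2, 6, 12 and 24 h (Section 7).

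**Step 1: is the rate limit reachable on NIV?** It depends on two things that the plan leaves open.

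| 12–16/min is | RR counts | Lowest RR on NIV | RR < 10 reachable? |
|---|---|---|---|
| Delivered rate | Total breaths | 12 (12 − 10 = 2 above the limit) | No |
| Delivered rate | Patient-triggered breaths | 0 | Yes |
| Target in a purely spontaneous mode | Either (they coincide) | 0 | Yes |

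The I:E ratio favours the delivered reading, because it fixes inspiratory time. At 12/min the cycle is 60/12 = 5 s, so inspiration lasts 5/(1+4) = 1.0 s to 5/(1+3) = 1.25 s. That describes a timed breath. The pressure-support line also fits a patient-triggered mode, so the documents do not settle it. Under the delivered reading, two staff could record 12 and 0 for the same patient without effort, and both would be following the protocol.

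**Step 2: does RR track ventilation if the rate is held?** Minute ventilation = RR × tidal volume.

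- At the target volume: 12 × 10 = 120 and 16 × 10 = 160 mL/kg/min. At the limit: 10 × 10 = 100 mL/kg/min.
- Tidal volume that gives 100 mL/kg/min with the rate held: 100/12 = 8.33 mL/kg (a 16.7% fall) or 100/16 = 6.25 mL/kg (a 37.5% fall).
- With an assumed 50% fall in tidal volume: 12 × 5 = 60 and 16 × 5 = 80 mL/kg/min, with no RR trigger.

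This is arithmetic on the plan's settings and does not predict what isoflurane does. Pressure support is titrated to volume, so staff may notice and correct a fall, but no safety event is defined on it.

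**Step 3: does the hypercapnia check discriminate?** Taken as a yes/no event, it is positive at entry in 20 of 20 patients by eligibility. A label already positive before the first dose cannot separate a drug effect from the entry condition. This step does not depend on ventilator mode.

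**Step 4: what can the Section 9.4 comparisons show?** For a two-sided paired t-test at 0.05 with 80% power, the detectable mean change is about 0.66 SD with 20 complete pairs and about 1.0 SD with 10. A shared rise in PaCO2 is therefore detectable. There are three limits:

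- The result is a group summary, so a few worsening patients can be offset by others who improve.
- There is no control arm, so NIV benefit and any isoflurane harm fall in the same mean.
- Successive samples are 2, 4, 6 and 12 h apart.

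**The case against.** The strongest reply is that the plan never calls 12–16/min a backup or mandatory rate. A rate setting and a lower alarm limit can coexist, and the limit can be met when NIV is off or disconnected. This stands. A reader might infer that Sections 6 and 8 flatly contradict each other and that the limit has no sensitivity at all. The documents support that only if the rate is delivered and RR means total rate.

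A reader might also infer that the trial cannot show sedation-induced hypoventilation. The documents do not support this. Section 9.4 compares serial gases with baseline, the ABG review also covers hypoxemia, and oximetry is continuous. RASS ≤ -3 stops sedation and counts as failure, as does intubation, and SAEs go to the DSMC within 24 hours. The ABG line describes a review and does not define a yes/no event. The interim rule in Section 9.6 uses failure and SAE rates, so an RR-event count does not drive it directly. The primary analysis in Section 9.3 is unaffected.

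These safeguards only partly fill the gap. FiO2 is titrated to a saturation range, which can blunt oximetry. Neither the failure definition nor the interim thresholds contain a CO2, pH or RR criterion. Nothing else in the plan gives a per-patient definition of worsening ventilation.

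**Conclusion.** The concern holds in a conditional form. If 12–16/min is delivered by the machine and RR means total rate, the limit sits 2 breaths/min below the lowest rate possible on NIV, and a zero count of respiratory depression says little about isoflurane. The first condition is the natural reading but is not stated. The second is an assumption, since no section defines RR. If either fails, the limit is reachable and what remains is an undefined term.

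The hypercapnia half needs neither assumption: as a per-patient event it does not discriminate, because eligibility makes it positive in all 20 patients. Worsening PaCO2 remains visible, as a group change at four time points.

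This is more than missing detail. In a trial with safety as an objective, following the plan on its natural reading could produce a falsely reassuring count.

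**What to change.** - **Sections 6 and 8:** reconcile them by stating the ventilator mode, whether 12–16/min is delivered or a target, and which RR the limit counts. The clinical rule itself is for the investigators to decide.
- **Section 7 and the CRF:** record patient-triggered and total RR separately, so that either definition can be tabulated.
- **Sections 8 and 9.4:** report ABG safety per patient as change from that patient's own baseline at 2, 6, 12 and 24 h, using the samples already scheduled. Any limits should be set by the investigators and fixed in advance.
- **Section 9.6:** give the DSMC both the RR data and the per-patient ABG changes at the 10-patient review.

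The cost is protocol wording and one extra CRF field; no new blood samples are needed. The downside is that more respiratory events may be reported.

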9.6 Interim Analysis

- After 10 patients, DSMC reviews safety: if > 50% failure or SAE rate > 20%, consider early termination.

10. Data Management and Quality Assurance

- Case report forms (CRFs) will capture all assessments.
- Data entry into secure electronic database with audit trail.
- Regular monitoring visits by Clinical Research Associate (CRA).
- Query resolution within 72 hours.

11. Ethics and Informed Consent

- Approval by Institutional Ethics Committee.
- Conducted per ICH-GCP and Declaration of Helsinki.
- Written informed consent obtained prior to any study procedure.
- Confidentiality maintained; data anonymized.

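### FiO2 is titrated to an SpO2 target but neither FiO2 nor NIV support is scheduled for recording, so the planned oxygenation comparison can miss a loss of gas exchange offset by more oxygen

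*Combined protocol and SAP*

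**What the plan says.** - **Titration (Section 6, Intervention).** FiO2 is "30–40% (titrate to SpO_2 88–94" per cent. Pressure support is "8–20 cm H₂O (titrated to 10 mL/kg IBW". PEEP also has a permitted range, 4–6 cm H₂O.
- **Objective (Section 3.2).** "Monitor changes in vital signs and arterial blood gas (ABG) parameters at baseline, 2, 6, 12, and 24 hours". The synopsis lists ABG changes under safety.
- **Schedule (Section 7).** The rows are "Vital signs (HR, BP, RR"), ABG parameters, RASS, VAS comfort and intervention failure. FiO2, SpO2, pressure support, PEEP and tidal volume have no row. The content of the ABG row is not defined.
- **Data capture (Section 10).** "Case report forms (CRFs) will capture all assessments". Nothing there extends capture to ventilator settings.
- **Analysis (Section 9.4).** For "Continuous variables (vitals, ABG, RASS, VAS") the test is: "Paired t-test (or Wilcoxon signed-rank) comparing baseline vs. each time point". No PaO2/FiO2 ratio is named, nor any adjustment for settings.
- **Bedside safety (Section 8).** Pulse oximetry is continuous, and ABGs are reviewed for raised CO2 or low oxygen. This section does not ask for settings to be recorded either.

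**The concern.** When a variable is held near a target by adjusting an input, its change from baseline partly reflects how well the adjustment worked. The underlying state shows in the input needed to stay on target. Here the controlled variable is oxygenation and the input is FiO2. The plan tests the first and does not schedule the second.

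ABG change is one of the study's safety outcomes, and the design is single-arm, so no concurrent group under the same titration rule could expose an effect of settings. A report of unchanged PaO2 after isoflurane could mean that gas exchange was stable, or that it worsened and oxygen was increased. The planned comparison cannot tell these apart.

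PaCO2 and pH have a weaker form of the same problem. If pressure support differs between baseline and a later sample, part of any change in PaCO2 may belong to the support. A fall could be credited to isoflurane, or a rise could be blunted.

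**Working it through.** **1. The plan's own figure.** The plan gives no expected value, SD or power for any ABG variable. Its only design figure is N = 20 (Section 9.1: 50% against 20%, 80% power, two-sided 5%), which limits each paired test to 20 pairs. As a one-sample comparison it reproduces:

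n = [1.960 × √(0.5 × 0.5) + 0.842 × √(0.2 × 0.8)]² / (0.5 − 0.2)² = 19.26, rounded up to 20.

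This point does not dispute that figure.

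**2. Where FiO2 appears.** It is titrated in Section 6, absent from the Section 7 schedule, and absent from the variables analysed in Section 9.4. Pressure support and PEEP follow the same path.

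**3. How much can be hidden at constant PaO2.** With PaO2 = P at both times and FiO2 moving from F0 to F1:

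(P/F1) / (P/F0) = F0/F1

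P cancels, so the percentage depends only on FiO2. The largest permitted upward move is 0.30 to 0.40:

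0.30/0.40 = 0.75, a fall of 25%, with a paired PaO2 difference of 0.

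| PaO2 at both times (assumed, mmHg) | PaO2/FiO2 at 0.30 | PaO2/FiO2 at 0.40 |
|---|---|---|
| 55 | 183 | 138 |
| 60 | 200 | 150 |
| 70 | 233 | 175 |

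A patient who starts above 0.30 has less room. From 0.35 the most that can be hidden is 1 − 0.35/0.40 = 12.5%. Once FiO2 reaches 0.40, further loss must appear as falling PaO2.

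**4. What this does to the paired test (illustration only).** The documents give no PaO2 level or SD, so all of these inputs are assumptions:
- 20 patients and 20,000 simulated trials per row and scenario;
- target PaO2 62 mmHg, with measurement SD 4 mmHg;
- FiO2 set to reach the target within 0.30–0.40;
- SD of within-patient change in log PaO2/FiO2 of 0.10 or 0.15;
- true PaO2/FiO2 at baseline centred on the value needing FiO2 0.30 or 0.32.

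The entries are the percentage of trials in which a two-sided 5% paired t-test rejects. The three values are, in order: start 0.30 with SD 0.10; start 0.30 with SD 0.15; start 0.32 with SD 0.10.

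| True fall in PaO2/FiO2 | Test on PaO2 | Test on PaO2/FiO2 |
|---|---|---|
| 0% | about 5 in each | about 5 in each |
| 10% | 20 / 26 / 6 | 91 / 72 / 91 |
| 15% | 24 / 40 / 10 | >99 / 98 / >99 |
| 20% | 31 / 59 / 29 | >99 in each |
| 25% | 60 / 83 / 83 | >99 in each |

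For a 15% loss, PaO2 at fixed FiO2 would fall by 0.15 × 62 = 9.3 mmHg. Under titration the simulated mean fall was 0.9 to 3.0 mmHg. At 25% the PaO2 test recovers much of its power because many patients have reached the FiO2 cap.

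**5. PaCO2 and pH.** No Section 6 setting is titrated to either. Pressure support is "titrated to 10 mL/kg IBW", which is a tidal-volume target. The link to PaCO2 is indirect, and no comparable ceiling can be derived from the documents.

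**The case against.** Several points on the other side stand and limit the claim.

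- **Only oxygenation is titrated to a target.** A reader might infer that all the planned ABG tests merely measure the titration. The documents do not support that. If tidal volume and rate stay near their Section 6 values, a rise in PaCO2 can still show, and CO2 is central in a population enrolled with hypercapnic failure.
- **The plan does not name PaO2.** It refers only to ABG and ABG parameters. A site may note FiO2 with the sample, and a ratio is not excluded. But nothing requires either, and pressure support and tidal volume are not blood-gas results.
- **Missing from the schedule is not the same as unrecorded.** A reader might infer that the settings leave no trace and that the gap could never be repaired at analysis. The documents do not say what source records exist. Excluding major protocol violations from the per-protocol set (Section 9.2) might itself need settings data.
- **The size is a ceiling.** The 25% needs FiO2 to move from floor to cap with PaO2 unchanged. SpO2 may vary over a six-point band, so PaO2 is not clamped. Pressure support of 8–20 cm H₂O is a permitted range (20/8 = 2.5). A reader might take that as a 2.5-fold change within a patient, but it may only reflect differences between patients.
- **Safeguards exist.** Section 8 monitoring may catch acute deterioration, and intubation counts in the primary endpoint. Neither replaces FiO2 in the analysis: SpO2 is the quantity being held on target, and the ABG outcome is there to show deterioration short of intubation.
- **Yield is limited.** In a single-arm study a change in PaO2/FiO2 still cannot be attributed to isoflurane rather than to NIV or the course of the exacerbation. Recording FiO2 makes the change visible but does not explain it.

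**Conclusion.** The concern holds for oxygenation. Followed as written, the plan can report no change in PaO2 while PaO2/FiO2 falls by up to 25%. That ceiling follows from the protocol's own FiO2 limits at constant PaO2 and needs no outside figure. The loss of power in the paired test is illustrative only: under the stated assumptions, a true 15% fall is detected in about 10–40% of trials on PaO2, against 98% or more on PaO2/FiO2.

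For PaCO2 and pH the supported statement is narrower: their change is hard to interpret without the concurrent pressure support.

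This affects a secondary safety objective. The primary analysis and the sample size are untouched. It is a cheap improvement, best made before data collection, because the documents give no assurance that settings could be recovered later.

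**What to change.** 1. **Section 7.** Add FiO2, SpO2, pressure support, PEEP and tidal volume at baseline, 2, 6, 12 and 24 hours, read when the ABG is drawn, with matching CRF fields.
2. **Sections 3.2 and 7.** List which ABG parameters are collected.
3. **Section 9.4.** Make PaO2/FiO2 the oxygenation measure for the paired comparison, and summarise PaO2 and FiO2 as well. Report change in pressure support beside change in PaCO2 and pH.
4. **Baseline.** State whether the baseline ABG and settings are taken on NIV before isoflurane starts. If baseline precedes NIV, change in pressure support has no comparable starting value.
5. **Reporting.** State that the single-arm design does not allow a change in PaO2/FiO2 to be attributed to isoflurane.

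The cost is a few values read from the ventilator and monitor at five existing times, plus SAP wording. The downside is minor extra data entry. No new procedure is needed, and no change to the titration rule is implied.

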Study Protocol and Statistical Analysis Plan

Isoflurane Sedation Using AnaConDa® Device with Non-Invasive Ventilation for Acute Exacerbation of COPD

**Protocol version 2.0
Dated 04.12.2022**

1. Protocol Synopsis

Title	Isoflurane Sedation Using AnaConDa® Device with Non-Invasive Ventilation for Acute Exacerbation of COPD
Study Design	Prospective, single-arm, interventional pilot study
Study Population	Adult patients (≥ 18 years) with acute exacerbation of COPD requiring NIV
Sample Size	20 patients (interim analysis after 10 enrollees; final analysis planned on 20)
Intervention	Isoflurane sedation via AnaConDa® device during NIV
Primary Objective	Incidence of intervention failure (intubation or excessive sedation)
Secondary Objectives	Safety (vitals, ABG changes), sedation depth (RASS), patient comfort (VAS)
Duration	24 hours of sedation monitoring; follow-up until discharge or intubation
Ethics Approval	BREC 23/121 (20.03.2023), in accordance with ICH-GCP and Declaration of Helsinki

2. Background and Rationale

Acute exacerbations of COPD (AE-COPD) frequently lead to hypercapnic respiratory failure, where non-invasive ventilation (NIV) reduces intubation and mortality risks. However, NIV intolerance due to agitation or dyssynchrony often necessitates invasive ventilation, with attendant complications. Volatile anesthetics like isoflurane, delivered via AnaConDa®, offer rapid, titratable sedation with bronchodilatory effects and minimal accumulation. Preliminary ICU studies suggest improved hemodynamics and faster recovery with inhalational sedation, but data in the NIV setting are lacking. This pilot protocol aims to assess feasibility and safety of isoflurane sedation via AnaConDa® in AE-COPD on NIV.

3. Objectives

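### Section 8 defines hypotension, bradycardia and respiratory depression, but Section 9 plans no count of the patients who cross those limits

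*Combined protocol and SAP*

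**What the plan says.** Section 2 says that the pilot "aims to assess feasibility and safety of isoflurane sedation". The synopsis words the secondary objectives as "Safety (vitals, ABG changes), sedation depth (RASS), patient comfort (VAS", so safety is framed there as change in measurements.

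Section 8 sets three numerical limits. It says to "Monitor for hypotension" at SBP < 90 mmHg, and gives HR < 50 bpm for bradycardia and RR < 10 breaths/min for "respiratory depression". Oximetry and ECG are continuous, and blood pressure is scheduled as "non-invasive BP every 15 minutes for first hour, hourly thereafter". Section 8 gives no reading schedule for RR; the only one is the visit table in Section 7. The synopsis gives the period as "24 hours of sedation monitoring; follow-up until discharge or intubation".

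Section 9.4 places vital signs under "Continuous variables (vitals, ABG, RASS, VAS". They are summarised by mean and SD or median and IQR, with a paired t-test or Wilcoxon test against baseline at each time point. Sections 3.2 and 7 fix those points at 2, 6, 12 and 24 h. The categorical line of 9.4 begins "Categorical variables (intubation, excessive sedation" and names nothing further. Section 9.3 estimates the proportion with intervention failure, with a Wilson interval. Section 9.6 has the DSMC review safety after 10 patients, with triggers at failure above 50% or an SAE rate above 20%.

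**The concern.** The protocol decides in advance what counts as a low pressure, a slow heart rate and a slow respiratory rate, and has staff watch for them. The analysis plan then never uses those definitions. A group mean or median at four visits does not say how many patients crossed a limit, and it ignores anything that happened between visits. The first hour is when blood pressure is taken most often, yet the first analysed point after baseline is 2 h.

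The trial could therefore report little average change in blood pressure although several patients had been hypotensive, and still have followed its plan. A later study would want per-patient event rates from this pilot, and the plan does not commit to producing them. Nothing bars reporting them afterwards, but what to report would then be chosen after the data are seen.

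**Working it through.** **1. The plan's own figure.** N = 20 matters here only as a denominator. It reproduces as a one-sample test of 50% against 20%, two-sided 5%, 80% power: n = ((1.96 × √(0.5 × 0.5) + 0.8416 × √(0.2 × 0.8)) / 0.30)² = 19.26, rounded up to 20. Nothing below changes it.

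**2. Events against analyses.**

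| Event | Defined or named in | Analysis in Section 9 |
|---|---|---|
| Intubation | 3.1 | 9.3 (part of failure), 9.4, Kaplan–Meier curve |
| RASS ≤ −3 | 3.1 | 9.3 (part of failure), 9.4 |
| SAE | 8 | Rate at the interim, 9.6 |
| SBP < 90 | 8 | None |
| HR < 50 | 8 | None |
| RR < 10 | 8 | None |

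**3. Share of blood pressure readings used.** Section 8 implies 4 readings in the first hour and 23 hourly readings from 2 to 24 h: 4 + 23 = 27. Section 9.4 uses those at 2, 6, 12 and 24 h: 4/27 = 14.8%. None of the 4 first-hour readings is among them. This figure is for blood pressure only.

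**4. Brief episodes.** Assume that an episode of length d hours (d from 0.25 to 1) starts at a uniformly random time in the 24 h. The four visits catch 4d/24. The Section 8 schedule catches every episode that starts in the first hour and a fraction d afterwards: (1 + 23d)/24.

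| Episode length (assumed) | Four visits | Section 8 schedule |
|---|---|---|
| 15 min | 1/24 = 4.2% | 6.75/24 = 28.1% |
| 30 min | 2/24 = 8.3% | 12.5/24 = 52.1% |
| 60 min | 4/24 = 16.7% | 24/24 = 100% |

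**5. Group test as an event detector (illustration).** Assume that k of 20 patients are 40 mmHg lower at a visit, the others are unchanged on average, and the SD of change is 15 mmHg. The mean shift is −40k/20 mmHg. In 20,000 simulated trials per case, the paired t-test gave p < 0.05 as follows.

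| k | Mean shift (mmHg) | Significant |
|---|---|---|
| 1 | −2 | 5% |
| 2 | −4 | 9% |
| 3 | −6 | 16% |
| 4 | −8 | 27% |

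None of these inputs comes from the documents. The table shows only that a test of the mean is a weak way to find individual events.

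**6. What a count would give.** The Wilson interval is (p + z²/2n ± z√(p(1−p)/n + z²/4n²)) / (1 + z²/n), with z² = 3.84.

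- 3/20: 15%, interval 5.2% to 36.0%.
- 0/20: upper limit z²/(n + z²) = 3.84/23.84 = 16.1%.
- 0/10, at the interim: 3.84/13.84, about 28%.

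The chance of at least one affected patient among 20 is 1 − (1 − π)²⁰: 64%, 88% and 99% for assumed true rates π of 5%, 10% and 20%.

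**The case against.** The best defence is that the analysis matches the objective. The synopsis and Section 3.2 describe safety as change in vital signs and blood gases at fixed times, and 9.4 analyses that. Section 4 says that continuous monitoring guides titration, so the Section 8 limits may be meant for the bedside only. This stands to the extent that the plan does not contradict itself. It does not supply an event rate, which a pilot with a safety aim needs, and the SD or IQR that 9.4 also reports does not replace a count.

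Three stronger readings are tempting, and the documents do not support them.

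- A reader might infer that safety events will be absent from the results. Intubation and RASS ≤ −3 form the primary endpoint and reappear in 9.4, and the SAE rate is reviewed at the interim.
- A reader might infer that the DSMC will not see threshold events. Section 9.6 names two triggers for considering termination. It does not say what the DSMC report contains or leaves out.
- A reader might treat the simulation or the 30-minute episode as an estimate for this trial. Both rest on assumed inputs.

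Objections to counting also have force. Blood pressure is hourly after the first hour, so brief episodes will be missed. RR has no schedule outside the Section 7 visits. Section 6 lists RR 12–16 among the ventilator settings, and the documents do not say whether recorded RR is the patient's own rate. A patient may already be below a limit at baseline. These points shape the table and how it is read; they do not remove the need for it.

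**Conclusion.** The concern holds for the three Section 8 threshold events and no further. Section 9 specifies no analysis of how many patients cross SBP < 90, HR < 50 or RR < 10. Vital signs enter only as group-level change at four times, which uses 4 of about 27 scheduled blood pressure readings after the start (15%) and none from the first hour. Individual or transient events can therefore go unreported.

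The 4/27 follows from the schedules if sedation lasts the full 24 h. The catch rates for brief episodes depend on assumed length and uniform timing, and the t-test figures on an assumed fall and SD. The conclusion needs neither, because it follows from reading Section 8 against Section 9. The change is worth making before analysis. It leaves the primary analysis and the sample size untouched.

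**What to change.** In 9.4, add as safety outcomes the number and proportion of treated patients (the ITT set of 9.2) with at least one recorded reading below each Section 8 limit, and below any of them, during the sedation period up to 24 h. Give Wilson 95% intervals, the method already used in 9.3.

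- Take SBP and HR from the Section 8 monitoring record. Because ECG is continuous, state which HR values count as recorded.
- Take RR from whatever RR readings are recorded, at least the Section 7 visits, and name that source.
- Flag patients already below a limit at baseline.
- Include the same table in the DSMC review at 10 patients.
- State that the counts are a lower bound. With hourly blood pressure after the first hour, about 52% of 30-minute episodes would be caught under uniform timing.

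The cost is a few CRF fields and one table. Monitoring, limits, clinical actions and the primary endpoint stay as they are.
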